6.3 PATIENT SETS ANALYSED

Treated set (TS):

This patient set includes all patients enrolled in the trial who were documented to have taken at least one dose of study medication.

Dose finding cohort treated set:

This patient set includes all patients enrolled in dose finding cohort of the trial who were documented to have taken at least one dose of study medication.

MTD Expansion cohort treated set:

This patient set includes all patients enrolled in expansion cohort who must satisfy the following criterion:

- Patients' tumour must be tested for positivity on 2 of the following tests: EGFR IHC>150 and/or HER2 IHC>0 and/or EGFR FISH positive and/or HER2 DDISH positive.

or

- Patient will have proven genomic, transcriptomic or proteomic alterations which are not defined above.

and

- Patients who were documented to have taken at least one dose of study medication.

PK analysis set (PKS):

This set includes all patients in the treated set (TS) who provided at least one PK endpoint that was not excluded due to a protocol deviation relevant to the evaluation of PK or due to PK non-evaluability. Thus, a patient will be included in the PKS, even if he/she contributes only one PK parameter value for one period to the statistical assessment. Descriptive and model based analyses of PK parameters will be based on the PKS.

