7.3 PLANNED ANALYSES

All patients who receive at least one dose of afatinib will be included in the analysis for safety and efficacy and they are defined as treated set.

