7.3.1 Primary analyses

Dose finding part:

In order to determine the MTD, the number of patients with DLT deemed to be related to administration of afatinib will be assessed based upon the patients in dose finding part of the trial. (See [Table 4.1.4.1:2](#)). The advanced disease of the patients in this trial makes it possible that significant adverse events, including events that would qualify as DLT, will occur, but will not be caused by afatinib. The MTD will be determined as the highest dose at which no more than 1/6 patients experienced DLT considered related to afatinib. (See [Table 4.1.4.1:1](#))

Proprietary confidential information.

© 2017 Boehringer Ingelheim International GmbH or one or more of its affiliated companies. All rights reserved.

This document may not - in full or in part - be passed on, reproduced, published or otherwise used without prior written permission.

Pharmacokinetics is a primary endpoint for the dose finding part. For details see [Section 7.3.5](#)

MTD expansion cohorts/Phase II part:

OR will be assessed when the last patient enrolled in the MTD expansion cohorts/Phase II part will be evaluable for efficacy.

Each patient will be assigned to one of the following categories based on investigator's assessment according to the institutional response evaluation criteria for the given tumour type, irrespective of protocol violation or missing data:

- CR (complete response)
- PR (partial response)
- SD (stable disease)
- PD (progressive disease)
- Not evaluable (not assessable, insufficient data)

Objective response is defined as CR and PR.

If the International Criteria for Neuroblastoma Response Criteria (INRC) ([R14-2418](#)) is used, each patient will be assigned to one of the following categories:

- CR (complete response)
- VGPR (very good partial response)
- PR (partial response)
- MxR (mixed response)
- NoR (no response)
- PD (progressive disease)

The objective response is then defined as CR, VGPR, PR or MxR.

OR will be tabulated and provided with the proportion and the exact 95% confidence interval based on all treated patients in the MTD expansion cohorts/Phase II part.

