6.2 IMPORTANT PROTOCOL DEVIATIONS

A protocol deviation is important if it affects the rights or safety of the study patients, or if it can potentially influence the primary outcome measurements in a non-negligible way. Patients with important protocol deviations (IPDs) that could potentially impact the evaluation of the primary endpoint(s) will be excluded.

The different categories of IPDs are defined in Table 6.2: 1. IPDs will be reviewed at Medical Quality Review Meetings (MQRMs) conducted periodically during the trial. A list of protocol deviations will be discussed at the report planning meetings (RPMs). If the data show other IPDs, this table will be supplemented accordingly at MQRMs or RPMs or through team review of the protocol deviation log. The decision whether a patient will be excluded from the analysis will be made at the final RPM prior to DBL.

Table 6.2: 1 Important protocol deviations

Category/ Code	Description	Comment/Example	Excluded from	Manual/ Automatic
A	Inclusion/Exclusion Criteria			
A1				
A1.1	Laboratories measurements	Exclusion criteria 13,14,15	None	Automatic
A1.2	Forbidden concomitant diagnoses	Exclusion criteria 4,5,7,9,10,11,12	None	Automatic
A1.3	Female patients who are pregnant or doing breast feeding at baseline	Exclusion criteria 6	None	Automatic
A1.4	Prohibited concomitant medications, radiotherapy and surgery	Exclusion criteria 1,2,3, 8	None	Automatic
A2				Automatic
A2.1	Patient does not have trial diagnosis	Inclusion criteria 1	None	Automatic
A2.2	Patient did not recover (to CTCAE grade 1 or baseline) from any acute toxicity resulting from prior anti-cancer treatment (except alopecia)	Inclusion criteria 4	None	Automatic
A2.3	Patient did not have Lansky/Karnofsky (depending on age) scores $\geq 50\%$ assessed within 2 weeks prior to enrolment.	Inclusion criteria 8	None	Automatic
A2.4	Patient has LVEF $< 50\%$	Inclusion criteria 12	None	Automatic
A2.5	Required ErbB pathway deregulation absent	MTD Expansion Cohort: Inclusion criteria 1 or 13	None	Automatic
A2.6	Patient age at study start not between ≥ 2 to < 18 years Patient age at study start not between ≥ 1 to < 18 years	Dose finding cohort: Inclusion criteria 3 MTD expansion cohort: Inclusion criteria 3	None	Automatic
A2.7	No tumour tissue available (exception of DIPG)	MTD Expansion Cohort: Inclusion criteria 7	None	Automatic

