7.4 PRIMARY ENDPOINT(S)

7.4.1 Dose Finding Part:

One of the primary objectives is to assess the MTD based on the number of patients presenting DLTs during the MTD evaluation period. Therefore, an overall summary of DLTs (see CTP Section 4, Table 4.1.4.1.2 for the definition of DLTs) which occurred during the MTD evaluation period will be provided for each dose cohort from the dose finding cohort treated set. Patients who were replaced within the MTD evaluation period will be excluded from the determination of the MTD but will be considered for all other safety evaluations.

A summary of the number of patients with DLTs overall in any course will be also given by initial treatment and displayed in a similar format to the summary of DLTs occurring in the MTD evaluation period.

The determination of the MTD is based on a Rolling 6 design as illustrated in Section 4, Table 4.1.4.1:1 of the CTP. The MTD is defined as the highest dose at which no more than 1/6 patients experienced DLT considered related to afatinib during the MTD evaluation period. Refer to CTP 7.3.1 for further details on MTD evaluation.

Analysis of the standard PK endpoints is performed according to (2) and (8) as outlined in Section 7.3.5 of the CTP.

7.4.2 MTD expansion cohort part:

Objective response (OR) is defined as a best overall response of complete response (CR) or partial response (PR) based on investigator's assessment according to the institutional

response evaluation criteria for the given tumour type. If the International Criteria for Neuroblastoma Response Criteria (INRC) is used, OR is defined as complete response (CR), very good partial response (VGPR), partial response (PR) and mixed response (MxR). For further details on OR, please refer to CTP Section 7.3.1. The objective response rate will be calculated and reported as proportion of responders with 95% Clopper-Pearson CIs based on all treated patients. Objective response will be summarized regardless of confirmation.

Additional summary or listing may be provided for confirmed response. If only few patients (fewer than 5) achieved objective response, a detailed listing will be reported.

For objective responses, evaluated by institutional response evaluation criteria other than INRC, below confirmation rule for best overall response will be considered.

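### SAP 6.3, read literally, makes biomarker positivity a condition of the expansion treated set, which conflicts with the protocol's dose-only set and leaves the primary ORR denominator ambiguous (minor)

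*SAP*

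**What the plan says.** **Protocol.** Section 7.3 sets a single condition for the treated set: "All patients who receive at least one dose of afatinib will be included in the analysis for safety and efficacy". Section 7.3.1 assigns every expansion patient a response category "irrespective of protocol violation or missing data", and gives the ORR with an "exact 95% confidence interval based on all treated patients in the MTD expansion cohorts/Phase II part".

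**SAP 6.3.** Three treated sets are defined. The overall set is dose-only: "This patient set includes all patients enrolled in the trial who were documented to have taken at least one dose of study medication". The dose-finding set is also dose-only. The expansion set differs: "This patient set includes all patients enrolled in expansion cohort who must satisfy the following criterion". The criterion that follows is that the patient's "tumour must be tested for positivity on 2 of the following tests", or that another genomic, transcriptomic or proteomic alteration is proven. A further 'and' then adds at least one documented dose.

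**SAP Table 6.2:1.** Code A2.5, "Required ErbB pathway deregulation absent", has the entry None in the column for the analysis set from which the patient is excluded.

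**SAP 7.4.2.** The ORR is "reported as proportion of responders with 95% Clopper-Pearson CIs based on all treated patients". No set from 6.3 is named, and the reader is sent to protocol 7.3.1 for further detail on OR.

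**SAP Section 4.** The list of changes to the planned analysis mentions biomarker-based recruitment but no biomarker-restricted analysis set.

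**The concern.** ORR is the primary endpoint of the expansion part, and its denominator should follow from the text without interpretation. Here it does not. Protocol 7.3, protocol 7.3.1 and Table 6.2:1 all keep a treated child who turns out to lack the required alteration. SAP 6.3, taken at its word, leaves that child out of the only treated set defined for the expansion part. A programmer who looks for the set that SAP 7.4.2 means would naturally choose that one, because the overall treated set also contains the dose-finding patients.

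If that happened, a figure labelled as based on all treated patients would be based on biomarker-eligible treated patients, a departure from the protocol that the SAP does not declare. Protocol 3.2 says the OR rate must be judged meaningful by experts and regulators before development continues, so the basis of the figure should be clear to them.

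This is separate from the general sentence in SAP 6.2 about excluding patients whose important deviations could affect the primary endpoint. Correcting that sentence would leave the wording of 6.3 unchanged.

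**Working it through.** The plan states no figure that depends on this definition, so there is nothing to reproduce. The check is a comparison of texts, followed by an illustration of size.

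**1. Where each text places a dosed expansion patient without the required alteration**

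| Text | Condition | Patient in the ORR denominator? |
|---|---|---|
| Protocol 7.3 | at least one dose | Yes |
| Protocol 7.3.1 | treated in the expansion part, violations disregarded | Yes |
| SAP Table 6.2:1, A2.5 | excluded from: None | Yes |
| SAP 7.4.2 | all treated patients, set not named | Depends on the set meant |
| SAP 6.3 expansion set | (2 of 4 tests positive or other proven alteration) and at least one dose | No, if this set is used |

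**2. Can such a patient exist?** Rarely. Protocol 4.1.2 requires central confirmation of ErbB deregulation for cohorts 1 to 4 and a laboratory report before study entry for cohort 5. But code A2.5 exists for this case, and protocol 3.3.4.1 foresees patients entered in violation of the criteria, each considered individually.

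**3. Size.** Assumptions: 38 treated expansion patients (the protocol gives up to 38 evaluable for OR), 4 responders, and 1 to 3 patients without the required alteration. The last two counts are not in the documents and are illustrative. ORR = x/n, with the Clopper-Pearson 95% interval from the 2.5% quantile of Beta(x, n − x + 1) to the 97.5% quantile of Beta(x + 1, n − x).

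| Denominator | x/n | ORR | 95% CI |
|---|---|---|---|
| Dose-only | 4/38 | 10.5% | 2.9 to 24.8 |
| One non-responder dropped | 4/37 | 10.8% | 3.0 to 25.4 |
| Two non-responders dropped | 4/36 | 11.1% | 3.1 to 26.1 |
| Three non-responders dropped | 4/35 | 11.4% | 3.2 to 26.7 |
| One responder dropped | 3/37 | 8.1% | 1.7 to 21.9 |

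Dropping three non-responders raises ORR by 11.4 − 10.5 = 0.9 points. Dropping one responder lowers it by 10.5 − 8.1 = 2.4 points. The intervals overlap almost entirely.

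With 8 responders, dropping four non-responders moves 8/38 = 21.1% (9.6 to 37.3) to 8/34 = 23.5% (10.7 to 41.2), a rise of about 2.5 points before rounding.

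**The case against.** The strongest reply is that the plan already keeps the patient in. SAP 7.4.2 says all treated patients and refers to protocol 7.3.1, SAP Section 3 says the SAP is based on protocol Section 7, and A2.5 excludes nobody. This stands to a large extent: a reader might infer that SAP 6.3 definitely removes these patients from the primary ORR, but the documents do not say so. Removal follows only if 7.4.2 means the 6.3 expansion set, which is not stated.

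A second reply is that the biomarker clause only repeats who is eligible for the expansion part. That is possible but strained. The clause is joined by 'and' to the dosing condition, and neither of the other two treated sets restates eligibility.

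A reader might also infer that the narrower set inflates the ORR because patients without the alteration would not respond. The documents do not support this: protocol 2.1 poses the druggability of deregulated ErbB receptors as a question for the trial. The ORR could move either way.

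Finally, a reader might point to a cohort of five, where losing one non-responder moves 1/5 = 20% to 1/4 = 25%. The arithmetic is right, but neither protocol 7.3.1 nor SAP 7.4.2 specifies an ORR by cohort, and five is a minimum.

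**Conclusion.** The conflict is real and the point is minor. SAP 6.3 as written disagrees with protocol 7.3 and 7.3.1 and with Table 6.2:1, and SAP Section 4 does not declare the difference. The consequence is an ambiguous denominator for the primary ORR. Neither a demonstrated exclusion nor a bias in a known direction has been shown.

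On the assumed counts with 4 responders and 1 to 3 non-responders dropped, the pooled ORR rises by at most 0.9 points; one dropped responder would lower it by 2.4. Pre-entry biomarker confirmation makes even these cases uncommon. Protocol 7.2 plans no hypothesis test, so no error rate is affected, and the safety analyses in SAP 7.8 use the overall treated set, which is dose-only.

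**What to change.** Amend the SAP as follows:

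- In 6.3, define the MTD Expansion cohort treated set as all patients enrolled in the expansion part with at least one documented dose.
- In 7.4.2, name that set as the denominator for the ORR.
- Keep biomarker status as deviation A2.5 only, with None retained in the exclusion column.
- If a biomarker-confirmed ORR is wanted, define it as a named sensitivity analysis on its own set.

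If the narrower set was intended for the primary analysis, SAP Section 4 should declare and justify it, and A2.5 and 7.4.2 should be aligned with it.

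The cost is SAP wording only; no data collection changes. Compared with the literal 6.3 set, the reported ORR may be slightly less favourable if any affected patient is a non-responder.

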 - 13 Imaging (CT or MRI for CNS tumours or soft tissue lesions) assessment is to be performed every 8 weeks until progression of disease. In case of objective response, the latter has to be confirmed 4 to 6 weeks after initial OR observation. Consecutive imaging assessment will be performed every 8 weeks. In exceptional cases when patients have been stable on treatment for at least 2 consecutive images (i.e. 16 weeks), imaging intervals may be extended to 12 weeks upon discussion between the investigator and the sponsor.
 - 14 Tumour marker(s) in urine or blood as indicated depending on tumour type (e.g. catecholamines (VMA/HVA, dopamine), NSE in neuroblastoma)
 - 15 Intra-patient dose escalation might be allowed as soon as the next higher dose tier is completed and considered safe (applicable to dose finding part only). A dose reduction can also be applied in case of drug-related toxicity (see [Section 4.1.4.3](#))
 - 16 New kit(s) of trial drug must be dispensed at visit 1 of each course. If needed (e.g. in case a dose adaptation has to be applied during treatment course), new kit(s) of trial drug might be dispensed outside of the planned visit schedule
 - 17 A full PK profile (extensive PK sampling) is to be taken at course 1, day 1: pre-dose before afatinib administration then 1h, 2h, 3h, 4h, 5h, 6h, 8h and 24h after administration and to be repeated at steady state on day8. In exceptional cases where extensive PK sampling is not possible, a limited sampling approach must be applied with blood sampling before, 1h and 3 h after afatinib administration. An additional trough sample is to be taken on day 15 to confirm steady state exposure to afatinib. In addition, trough CSF sampling (from Rickham, Ommaya reservoirs or from lumbar puncture performed for clinical reasons not related to the trial) may be taken on day 8 or later. This CSF sampling is optional. Each trough CSF sample has to be accompanied by a trough plasma sample taken at the same time-point. For further details on time points and sampling volumes, see [Section 5.5.2](#) and [Appendix 10.3](#).
 - 18 During the dose escalation part, a DLT confirmation fax has to be sent to the sponsor before start of course 2.
 - 19 AE/SAE after the 28-30 days FU period have to be reported only if considered relevant by the investigator.
-
- 22 Lansky for patients ≤ 12 years or Karnofsky for patients older than 12 years at time of informed consent

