5.5 DRUG CONCENTRATION MEASUREMENTS AND PHARMACOKINETICS

5.5.1 Pharmacokinetic endpoint(s)

Pharmacokinetics will be a primary endpoint for the dose escalation part and a secondary endpoint for the biomarker specific MTD expansion cohorts/Phase II part. Extensive plasma PK sampling is therefore crucial in this trial. Whenever possible, a full plasma PK profile will be taken after first dose and at steady state (e.g. after 8 days of treatment with afatinib). An additional trough sample will be taken on day 15 to confirm steady state exposure to afatinib. In exceptional cases and only if paediatric patients are by no means able to undergo extensive plasma PK sampling a limited sampling approach should be applied.

In addition, in patients carrying a Rickham- or Ommaya reservoir, or undergoing lumbar puncture for clinical reasons not related to the trial, trough CSF sampling may be performed on day 8 or later to investigate CNS exposure to afatinib. This procedure is optional. The trough CSF PK sample must be accompanied by a trough plasma PK sample taken at the same time-point.

In any case, it must be attempted to keep all patients on their starting formulation for the first treatment course. This will be crucial for the MTD determination and PK assessment during first course.

In case patients' switch from tablet to liquid formulation or vice versa becomes necessary during treatment or if for any other reason (e.g. AE) plasma PK sampling cannot be performed as planned, plasma PK profiles may be obtained within treatment course 1 as deemed appropriate by the investigator and after consultation with the sponsor.

All details with respect to sampling procedures and time points are described in [Section 5.5.2](#) and tabulated in [Appendix 10.3](#).

Pharmacokinetics (PK) will be evaluated as follows:

- Non-compartmental analysis: PK parameters will include AUC, C_{max} , t_{max} and accumulation (or effective) half-life will be performed for all patients with extensive PK sampling
- Model-based analysis will be performed for all patients with sparse as well as extensive PK sampling

For further details regarding the PK analysis, please refer to [Section 7.3.5](#).

Proprietary confidential information.

© 2017 Boehringer Ingelheim International GmbH or one or more of its affiliated companies. All rights reserved.

This document may not - in full or in part - be passed on, reproduced, published or otherwise used without prior written permission.

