In the clinical trial report, afatinib plasma concentrations from patients who were not able to undergo extensive sampling, and for whom sparse sampling was performed, will be summarised by time point by descriptive statistics and, if feasible, graphically inspected.

Model based analysis

A model-based analysis over all available PK data (extensive and sparse sampling) will be performed.

Structure of the available population PK model

Based on existing afatinib PK models in adult patients having various solid tumours (studies 1200.1; .2; .3; .4 and 20 ([U12-1393](#)) and 1200.28; .32 and .33 ([U12-1394](#))), a model will be developed based on 1200.120 data in paediatric population.

Model development

A non-linear mixed effect modelling approach will be taken to conduct the analysis. The parameters of the model are defined by fixed effects, so called θ s and potential random effects (Inter (η) or intra-individual variabilities (κ)). These random effects are normally distributed around zero with a variance ω^2 . The combination of the fixed effects and random effects allow the estimation of individual parameters (P_i) as described in the following example equation:

$$P_i = \theta * \exp(\eta_i)$$

In addition, a residual variability, ε , adjusts the prediction of the model to the observed measurement. This residual variability is normally distributed with a variance σ^2 and can be described according to the following equation:

$$Y_{i,j} = \text{IPRED}_{i,j} + \varepsilon_{i,j}$$

where $Y_{i,j}$ is the j^{th} observation for i^{th} individual, $\text{IPRED}_{i,j}$ is the individual prediction of the model for the j^{th} observation of the i^{th} individual, $\varepsilon_{i,j}$ is the residual variability for the j^{th} observation of the i^{th} individual. In the current situation Y is the plasma concentration of afatinib. If possible First Order Conditional Estimation with Interaction (FOCE / INT) will be used for the complete model development. The data from all dose groups of this study will be used for model development.

Effect on Body weight on clearance and on volume of distribution will be evaluated, and the respective parameters (CL, V) will be scaled based on body weight.

Handling of missing data: Samples marked as no sample available (NOS) or non-valid result (NOR) will not be included in the dataset. Handling of missing PK data will be performed according to BI standards as stated in [Section 7.4](#) (MCS-36-472, current version).

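### SAP 6.3 bases model-based PK analyses on a set that requires a PK parameter value, which conflicts with the protocol's plan to model all sparse and extensive data

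*SAP*

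**What the plan says.** **SAP.** Section 6.3 defines the PKS as treated patients "who provided at least one PK endpoint that was not excluded due to a protocol deviation relevant to the evaluation of PK" or because of PK non-evaluability. It adds that a patient belongs to the set "even if he/she contributes only one PK parameter value for one period to the statistical assessment". The section ends: "Descriptive and model based analyses of PK parameters will be based on the PKS". The July 2020 entry in the SAP history table lists the PKS definition among the items updated.

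**Protocol, model-based analysis.** Section 5.5.1 says: "Model-based analysis will be performed for all patients with sparse as well as extensive PK sampling". Section 7.3.5 says: "A model-based analysis over all available PK data (extensive and sparse sampling) will be performed". The synopsis lists Cmax,ss, AUCtau,ss, CL/F and Vd/F from population modelling as PK criteria, again for patients with either type of sampling.

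**Protocol, NCA and sparse data.** Section 5.5.1 plans NCA for the extensively sampled: AUC, Cmax, tmax and "accumulation (or effective) half-life will be performed for all patients with extensive PK sampling". For patients who cannot have the full profile, Flow Chart footnote 17 says "a limited sampling approach must be applied with blood sampling before, 1h and 3 h after afatinib administration". Section 7.3.5 says that concentrations from patients "for whom sparse sampling was performed, will be summarised by time point by descriptive statistics". It plans no individual NCA parameter for them.

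**The concern.** The SAP decides who enters the model-based analyses by a derived quantity (a parameter value). The protocol decides it by the raw material of the model (concentrations, however sparsely sampled). A patient with sparse profiles alone has usable concentrations but no planned NCA parameter, so the two rules can give different answers for that patient.

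The population model is the only planned route to exposure estimates for sparsely sampled patients. Protocol 7.3.5 scales CL and V on body weight and uses the model to simulate steady-state exposure over the relevant age range. If patients who could not tolerate full sampling were left out, the model would rest on a narrower group than the protocol intends. A programmer following SAP 6.3 literally and one following protocol 7.3.5 could build different datasets.

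**Working it through.** No stated figure needs reproducing. The check sets the passages side by side and then counts samples.

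**Step 1. What counts as a PK endpoint?** SAP 5.2.2 lists four quantities for the expansion part: AUCtau,ss, Cmax,ss, tmax,ss and accumulation half-life. The synopsis gives the same four on its NCA line, for extensively sampled patients. The synopsis model line has Cmax,ss, AUCtau,ss, CL/F and Vd/F; of these, CL/F and Vd/F are not SAP endpoints. SAP 5.1 names AUCtau,ss and Cmax,ss as the primary PK endpoints of the dose finding part and gives no derivation method.

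**Step 2. Apply the PKS rule to a patient with sparse sampling only.**

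| Reading of PK endpoint | Does the patient qualify? | Consequence |
|---|---|---|
| NCA parameter (matches the SAP 5.2.2 list) | No: none is planned | Outside the PKS, so outside the analyses based on it |
| Model-derived Cmax,ss or AUCtau,ss also counts | Only after the model has been fitted with that patient's data | Circular: the set cannot be fixed before the analysis that uses it |

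Neither reading gives a rule that can be applied beforehand and also yields the population in protocol 5.5.1 and 7.3.5.

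**Step 3. Was a change declared?** SAP section 4 records the revised expansion cohorts and the corrected definition of duration of response. It records no change to the model population.

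**Step 4. Count what is at stake per patient** (protocol Appendix 10.3, plasma samples).

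- Extensive: pre-dose, 1, 2, 3, 4, 5, 6, 8 and 24 h = 9 on day 1, 9 on day 8, and 1 trough on day 15. 9 + 9 + 1 = 19.
- Sparse: pre-dose, 1 h and 3 h = 3 on day 1, 3 on day 8, and 1 trough on day 15. 3 + 3 + 1 = 7.
- One of the 7 is taken before the first dose and says little about exposure. That leaves 7 - 1 = 6.

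**Step 5. Illustrate the total.** The documents do not say how many patients were sparsely sampled. The shares below are assumptions, applied to the planned maximum of 17 + 38 = 55 patients.

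| Assumed share | Patients | Planned samples (x 7) |
|---|---|---|
| 5% | 2.75, about 3 | 21 |
| 10% | 5.5, about 6 | 42 |
| 20% | 11 | 77 |

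At 20%, planned samples total 11 x 7 + 44 x 19 = 77 + 836 = 913, so 77/913 = 8.4% of samples but 20% of patients.

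**The case against.** The strongest reply is that this is loose wording and that nobody is actually excluded.

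- **The SAP never says sparse data are left out.** This is true, and it matters. A reader might infer that the SAP has settled on dropping these children; the text does not support that. The synopsis allows a reading in which a sparse patient supplies a model-derived endpoint. That reading removes the exclusion but leaves the circularity.
- **The sentence may concern analyses of parameters, not the model fit.** The model in protocol 7.3.5 is fitted to concentrations, so the SAP sentence could mean something like the age-group comparison of PK parameters in SAP 7.5.2. This is possible. But the protocol uses the term model-based for the population PK analysis, and no other sentence in the public SAP text says which patients enter it.
- **The SAP defers to the protocol.** SAP section 3 says the plan is based on protocol section 7. SAP 7.4.1 points to protocol 7.3.5 for the standard PK endpoints, and SAP 6.6 points to 7.3.5 and 7.4 for missing PK data. These pointers favour the protocol's intent, but none defines the model population, and protocol 7.3.5 leaves further modelling detail to the SAP.
- **A Cmax could be read from the 1 h and 3 h samples.** Protocol 7.3.5 does define Cmax as the highest measured concentration, but under its extensive-sampling heading, and it plans no such value for sparse patients. Protocol 1.2 puts the adult peak mainly at 2 to 5 hours, so the true peak could be missed.
- **Few patients are affected.** This stands: the protocol reserves sparse sampling for exceptional cases.

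Some SAP section numbers (6.4, 7.6, 9) do not appear in the public text. Nothing is inferred from that.

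**Conclusion.** The passages conflict and should be reconciled. As written, the PKS rule either leaves patients with sparse sampling alone out of the model-based analyses or makes their membership depend on the model's own output. Neither matches the population the protocol states, and SAP section 4 declares no departure from it. Confidence is high that the wording is inconsistent. Whether any patient would in fact be excluded cannot be told from the documents.

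The size is probably small: 7 planned plasma samples per affected patient, 6 of them after the first dose, in an unknown number of patients. The totals above rest wholly on assumed shares. A reader might also infer that the loss would fall on the youngest, smallest or sickest children. The expansion part admits children from age 1 and sparse sampling is for those unable to undergo the full profile, so this is conceivable, but the documents do not record who was sparsely sampled. The point concerns the PK results only; no hypothesis test is planned, and the response and safety analyses are unaffected.

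**What to change.** In SAP 6.3:

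1. Keep the endpoint-based PKS, and limit it to the summaries of NCA parameters.
2. Add a population PK set: all treated patients with at least one valid afatinib plasma concentration after the first dose (later troughs included) and documented dosing and sampling times, whether sampling was extensive or sparse.
3. State that the model-based analysis in protocol 7.3.5 and the summaries of sparse concentrations by time point use that second set.

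The cost is a few lines of SAP text. No new data, visits or samples are needed, and the change restores the population the protocol already describes.
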